3.1 Objectives of Study

The primary objective of the study is:

- To evaluate the effect of long-term administration of multiple doses of subcutaneous (SC) injections of pegvaliase (also described as rAvPAL-PEG or pegvaliase) on blood Phe concentrations in subjects with phenylketonuria (PKU).

The secondary objectives of the study are:

- To evaluate the safety and tolerability of long-term administration of SC injections of pegvaliase in subjects with PKU.
- To evaluate the immune response to long-term administration of SC injections of pegvaliase in subjects with PKU.

The exploratory objectives of the study are:

- To evaluate the long-term relationship of diet and change in blood Phe concentration following administration with pegvaliase in subjects with PKU.

The Substudy objectives are as follows:

- To evaluate steady-state PK of pegvaliase in subjects who have achieved and maintained target blood Phe concentration and for whom no further dose modifications are planned.

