3.2 Study Design

This is a long-term extension of pegvaliase Phase 2 studies in subjects with PKU. The doses are planned to be in the same range as those tested in phase 2 (starting at 0.001 through 5.0 mg/kg/week or 2.5 mg through 375 mg/week), provided no dose-limiting toxicity is observed in a previous pegvaliase study.

Only subjects who completed a previous pegvaliase study will be enrolled into this study. Subjects enrolling into PAL-003 with no interruption in dosing from a previous pegvaliase

Proprietary and Confidential

	SAP PAL-003 Amendment 1 version 1.0	Page 7
---	-------------------------------------	--------

study may either continue their previous dosing regimen or begin this study at a higher dose level. Subjects who have had dosing interruptions between the previous pegvaliase study and PAL-003 must have their starting dose determined per the Sponsor's Medical Officer.

A PK substudy has been added to evaluate the steady-state PK of pegvaliase in up to 6 subjects who have achieved and maintained target blood Phe for at least 2 consecutive measurements and for whom no further dose modifications are planned. Subjects enrolled into the substudy will have additional pre-dose PK sampling performed.

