4 GENERAL ANALYSIS CONSIDERATION

Descriptive summaries of continuous variables will include the number of subjects (n), mean, standard deviation, median, minimum, and maximum. Descriptive summaries of categorical variables will include n and percent. Data from parent studies (PAL-002, PAL-004, 165-205) will be integrated together with data in PAL-003 for long term safety and efficacy analysis. The baseline value of an assessment is defined as the last available measurement prior to first administration of study drug from parent studies (PAL-002, PAL-004, 165-205), unless otherwise specified.

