4.5 Visit Window for Analysis

An assessment for a subject will be classified according to the study day of the assessment where it falls within a visit window. The windows are designated for each scheduled visit with a target day. If there are two or more assessments within a designated window, the assessment that is closest to the target day will be used for analyses. If the two closest assessments to the target day are equidistant from the target day, then the average of the two assessments will be used for analyses. If the measurement is a laboratory categorical variable, however, then the worse of the 2 equidistant measurements will be used.

Table 1 lists the visits assigned for the analyses of all assessments and the corresponding range of treatment days (window) during which a visit may have occurred by analysis parameter.

BIOMARIN®	SAP PAL-003 Amendment 1 version 1.0	Page 11
------------------	-------------------------------------	---------

Table 1: Visit Time Windows for the Treatment Period

Scheduled Time Point	Target Day	Visit Window
Baseline		Last measurement prior to pegvaliase administration from parent studies (PAL-002, PAL-004, 165-205)
Week 4	Day 22	Day 8 to Day 35
Week 8	Day 50	Day 36 to Day 63
Week 12	Day 78	Day 64 to Day 91
Week 16	Day 106	Day 92 to Day 119
Week 20	Day 134	Day 120 to Day 147
Week 24	Day 162	Day 148 to Day 175
...
Week 388	Day 2710	Day 2696 to Day 2723
Week 392	Day 2738	Day 2724 to Day 2751
Week 396	Day 2766	Day 2752 to Day 2779
Week 400	Day 2794	Day 2780 to Day 2807
Week 404	Day 2822	Day 2808 to Day 2835
Week 408	Day 2850	Day 2836 to Day 2863
Week 412	Day 2878	Day 2864 to Day 2891
Week 416	Day 2906	Day 2892 to Day 2919
Every 4 weeks		

Blood Phe concentration will also be summarized based on the data collected in PAL-003 and visits in [Table 2](#). For this analysis, the first study drug administration date for pegvaliase from PAL-003 is considered as study day 1 and is used as the reference date for the derivation of study day in data displays.

BIOMARIN®	SAP PAL-003 Amendment 1 version 1.0	Page 12
------------------	-------------------------------------	---------

Table 2: Visit Time Windows for the Treatment Period in PAL-003

Scheduled Time Point in PAL-003	Target Day in PAL-003	Visit Window in PAL-003
PAL-003 Baseline		Last measurement prior to pegvaliase administration from PAL-003
Week 4	Day 22	Day 8 to Day 35
Week 8	Day 50	Day 36 to Day 63
Week 12	Day 78	Day 64 to Day 91
Week 16	Day 106	Day 92 to Day 119

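### The PAL-003-only blood Phe summary and the CDF curve at PAL-003 entry pool uninterrupted subjects with subjects restarting after a dosing gap, so part of an apparent long-term fall can be restart effect

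*SAP*

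**What the plan says.** **The additional summary.** After setting out the integrated visit windows, SAP Section 4.5 adds: "Blood Phe concentration will also be summarized based on the data collected in PAL-003 and visits in" Table 2. The time axis is re-anchored for every subject: "For this analysis, the first study drug administration date for pegvaliase from PAL-003 is considered as study day 1". The first row of Table 2, labelled PAL-003 Baseline, is "Last measurement prior to pegvaliase administration from PAL-003". No condition is set on whether the subject was on or off drug at that measurement.

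**Who enters.** Section 3.2 describes two kinds of subject. The sentence on the first kind, divided by a page break, runs "Subjects enrolling into PAL-003 with no interruption in dosing from a previous pegvaliase" and then "study may either continue their previous dosing regimen or begin this study at a higher dose level". On the second kind it says: "Subjects who have had dosing interruptions between the previous pegvaliase study and PAL-003 must have their starting dose determined", with the decision left to the sponsor's medical officer.

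**The CDF.** Section 12 compares the distribution of Phe responses at three times: the beginning of PAL-003, the end of its first year and its end. It prefers this display to a categorical responder definition because the sample is small.

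**The integrated analysis.** Section 4 gives the general rule: "The baseline value of an assessment is defined as the last available measurement prior to first administration of study drug from parent studies", with room for exceptions. Section 4.4 takes Day 1 from the first parent-study dose. Section 12 defines baseline blood Phe as the value before the first parent-study dose and states no exception.

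**Gaps elsewhere.** Section 11 removes interruptions longer than 28 days from exposure duration. No comparable rule for dosing gaps is legible for blood Phe.

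**The concern.** The primary objective in Section 3.1 is "To evaluate the effect of long-term administration of multiple doses of subcutaneous (SC) injections of pegvaliase" on blood Phe. A reader will take the PAL-003-only summary, and the separation of the three CDF curves, as showing what happened to Phe during long-term treatment in PAL-003.

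The pooled starting point does not mean the same thing for everyone. For an uninterrupted subject, the last value before the first PAL-003 dose is an on-treatment value, and Week 4 is four more weeks of treatment. For a subject returning after a gap, the same row may be a value taken after some or all of the effect has worn off, and Week 4 is a restart week.

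If restarters return to their earlier level, the pooled mean falls even when no continuing subject has changed. The same mechanism could hide a loss of effect in continuing subjects, who carry the question of persistence.

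**Working it through.** **1. Window arithmetic.** The legible rows of Tables 1 and 2 follow target day = 7 × week − 6, with a window from target − 14 to target + 13. Week 4 gives 7 × 4 − 6 = 22 and Day 8 to Day 35, as printed. The windows are consistent; the issue is the anchor.

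**2. Does any legible rule separate the two groups?**
- Section 4.2 presents results by parent studies combined, PAL-003, and all combined. Part of it is redacted; what can be read refers to weekly or daily dose, not to dosing gaps.
- Section 12 leaves out efficacy data from 14 days after the last dose in the study. It states no exclusion for the interval between studies, and Table 2 keeps the last pre-dose value as its starting row.
- Section 11 deals with gaps for exposure duration only.

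So, as far as the text can be read, the pooling stands.

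**3. Illustrative size.** The SAP gives no share interrupted, gap lengths or Phe values, so every input here is an assumption. Let C = 600 µmol/L be the constant level of continuing subjects and the level to which restarters return, R the restarters' level at PAL-003 entry, and f the share interrupted.

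- Pooled entry mean = (1 − f) × C + f × R
- Pooled later mean = C
- Apparent fall = f × (R − C)

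| R (µmol/L) | f | Entry mean | Later mean | Apparent fall | % of entry mean |
|---|---|---|---|---|---|
| 900 | 10% | 630 | 600 | 30 | 4.8 |
| 900 | 25% | 675 | 600 | 75 | 11.1 |
| 900 | 50% | 750 | 600 | 150 | 20.0 |
| 1200 | 10% | 660 | 600 | 60 | 9.1 |
| 1200 | 25% | 750 | 600 | 150 | 20.0 |
| 1200 | 50% | 900 | 600 | 300 | 33.3 |
| 1500 | 10% | 690 | 600 | 90 | 13.0 |
| 1500 | 25% | 825 | 600 | 225 | 27.3 |
| 1500 | 50% | 1050 | 600 | 450 | 42.9 |

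At f = 0 the fall is zero for every R.

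**4. Does the choice of baseline matter?** Take a parent-study baseline of 1200 µmol/L (assumed) and R = 1200. Mean change at PAL-003 entry is (1 − f) × (600 − 1200) + f × (1200 − 1200) = −600 × (1 − f). This is −540, −450 and −300 for f = 10%, 25% and 50%; later it is −600 in each case. The drift is again 60, 150 and 300. The artefact comes from the mix of subjects at entry, not from which baseline is subtracted.

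**5. The CDF.** With R = 1200, the share of subjects at or below 600 µmol/L at entry is 1 − f, that is 90%, 75% or 50%, against 100% later. The curves separate by 10, 25 or 50 percentage points with no change in continuing subjects.

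**6. Masking.** With R = 1200, a rise of f × 600 / (1 − f) in continuing subjects would be cancelled in the pooled mean. At f = 25% this is 0.25 × 600 / 0.75 = 200 µmol/L.

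**7. After a split.** Under the assumptions of step 3, the uninterrupted group shows a change of 0 and the restart group shows C − R, that is −300, −600 or −900 µmol/L.

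**The case against.** The strongest reply is that this is an additional descriptive summary. The integrated analysis runs from the pre-drug parent-study baseline and Day 1. That stands. A reader might infer that the study's long-term conclusion rests on a reset baseline; the SAP does not support this.

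A reader might also infer that change from baseline will be computed from the PAL-003 entry value. Table 2 is a visit-window table, Section 12 gives the parent-study baseline for Phe without exception, and no text plans change from the PAL-003 row. The reset is certain only for Day 1 and the starting row. What remains is that Table 2 labels that row a baseline and needs to be reconciled with Section 12.

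Nor are the mean plots in Section 12 tied to Table 2, so the point covers the summary and the CDF, not a plot of Table 2 means.

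The figures are assumed throughout. Few or short gaps would bring the effect near zero. Uninterrupted subjects may also begin PAL-003 at a higher dose level, so a fall after entry could be a real dose effect in them. It would therefore be too strong to say that any fall comes wholly from restarters.

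Redaction in Section 4.2 means that other groupings cannot be fully excluded, and grouping by dose might separate restarters in part. Finally, the 28-day limit in Section 11 was written for exposure duration. Nothing in the SAP shows that the effect on Phe is lost at that point, and some mixing would remain with shorter gaps.

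These replies limit the reach and size of the point. They do not remove the pooling.

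**Conclusion.** The point holds for two displays: the PAL-003-only blood Phe summary on Table 2 visits, and the CDF curve at the beginning of PAL-003. Both pool on-drug and post-gap starting values, so a fall in observed means, or separation of the curves, can partly be restart of treatment rather than long-term effect.

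The illustrative fall is 60 to 300 µmol/L (9.1% to 33.3%) with restarters entering at 1200 µmol/L and 10% to 50% interrupted. Over entry values from 900 to 1500 it is 30 to 450 µmol/L. These figures also assume that continuing subjects stay at 600 and that restarters return fully to 600. They show what is possible, not what occurred. This is a low-cost improvement to descriptive displays; the Table 2 reset does not invalidate the integrated analysis.

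**What to change.** - **Sections 4.5 and 12:** present the Table 2 summary and the PAL-003 CDF also by dosing gap before the first PAL-003 dose (yes/no), with the gap length stated in advance. The 28 days in Section 11 is one option, not a limit that the SAP justifies for Phe.
- **Reading:** take persistence of effect from the uninterrupted group and label the other group as restart data. Note that some uninterrupted subjects may begin PAL-003 at a higher dose level.
- **Baseline:** reconcile Table 2 with Section 12 by stating that change is taken from the parent-study baseline, and relabel the PAL-003 Baseline row as the PAL-003 entry value.

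This needs SAP wording and one flag derived from dosing dates. No new data are collected and no clinical rule changes. The downside is smaller numbers per panel; keeping the pooled display beside the split limits that.

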4.6 Handling of Dropouts and Missing Data

Subjects who discontinued prematurely will not be replaced. To investigate the primary objective, last observation carry forward (LOCF) imputation approach will be used as sensitivity analyses.

	SAP PAL-003 Amendment 1 version 1.0	Page 13
---	-------------------------------------	---------

5 SUBJECT DISPOSITION

The number of subjects enrolled, the number of subjects who received study drug, the number of subjects who completed study, and the number of subjects in each analysis population (efficacy, safety, PK) will be summarized.

	SAP PAL-003 Amendment 1 version 1.0	Page 14
---	-------------------------------------	---------

6 END OF STUDY

For subjects who prematurely discontinued the study, the primary reason for discontinuation will be summarized. A subject listing of completion and early termination will be provided.

	SAP PAL-003 Amendment 1 version 1.0	Page 15
---	-------------------------------------	---------

7 PROTOCOL EXEMPTIONS AND DEVIATIONS

A major protocol deviation is defined as a departure from the approved study protocol that may impact the rights, safety, or welfare of the subjects or the integrity of the data, which will be summarized by deviation category.

A minor or administrative protocol deviation is defined as a departure from the approved study protocol that has minimum or no impact on the rights, safety, or welfare of the subjects or the integrity of the data. Minor protocol deviations will also be summarized by deviation category. For details regarding the classification of the deviations, please refer to the Study Specific Guideline for Managing Protocol Deviations.

Major and minor protocol deviations occurring during the parent studies (PAL-002, PAL-004, 165-205) and PAL-003 study will be summarized.

Subjects with protocol deviations during the parent studies (PAL-002, PAL-004, 165-205) and PAL-003 study will be provided in a listing. Subjects with inclusion or exclusion deviations during the parent studies (PAL-002, PAL-004, 165-205) and PAL-003 study will also be provided in a separate listing.

	SAP PAL-003 Amendment 1 version 1.0	Page 16
---	-------------------------------------	---------

8 DEMOGRAPHICS AND BASELINE CHARACTERISTICS

Subject characteristics and demographic information before the first dose of parent studies (PAL-002, PAL-004, 165-205) and the first dose of PAL-003 will be summarized. The demographics including age, age group (16 to <18 years of age, 18 to <66 years of age, \geq 66 years of age), gender, race and ethnicity will be summarized using descriptive statistics.

Subject characteristics will include height, weight, blood Phe concentration, intake of protein and dietary Phe, body mass index (BMI), BMI group ($<25 \text{ kg/m}^2$, $\geq 25 \text{ kg/m}^2$ and $<30 \text{ kg/m}^2$, $\geq 30 \text{ kg/m}^2$), and immunogenicity status (positive, negative, or titer value).

	SAP PAL-003 Amendment 1 version 1.0	Page 17
---	-------------------------------------	---------

9 MEDICAL HISTORY

Subject's past medical history and surgeries prior to parent studies (PAL-002, PAL-004, 165-205) and prior to PAL-003 were collected as general medical history. General medical history will be summarized by system organ class (SOC). A subject listing of each subject's medical history collected at the Screening Visit will also be provided.

	SAP PAL-003 Amendment 1 version 1.0	Page 18
---	-------------------------------------	---------

10 PRIOR AND CONCOMITANT MEDICATIONS/PROCEDURES

Prior and concomitant medications taken prior to, on or after the first dose of pegvaliase will be summarized for all enrolled subjects. For analysis purposes, the following definitions will be used to determine prior and concomitant medications:

- Prior medications: any medications taken within 30 days prior to the screening and prior to the initial pegvaliase administration date
- Concomitant medications: any medications initially taken on or after the initial pegvaliase administration date
- Prior and concomitant medications: any medications taken both prior to the initial pegvaliase administration date and on or after the initial pegvaliase administration date will be reported both as prior and concomitant medications. Therefore, any medications taken prior to the pegvaliase first dose date where the stop date is reported as “continuing” will be considered both as prior and concomitant medications.

In the event the start date of a medication is completely missing, the start date will be imputed as the first dose date if the stop date is in the same year or later than the first dose date.

In the event the start date of a medication is partial, the following imputation rules will be applied:

- If only day is missing, then the start date will be imputed as the first day of the month, if the year and month is after the first dose year and month. If only day is missing, then the start date will be imputed as the last day of the month, if the year and month is prior to the first dose year and month. If month is the same as the month of first dose of pegvaliase then the start date will be imputed as the first dose date of pegvaliase.
- If only year is non-missing, then the start date will be imputed as the first day of the year if the year is after the year of first dose. If year is the same as the year of first dose of pegvaliase then the start date will be imputed as the first dose date of pegvaliase. If year is before the year of first dose of study drug then the start date will be imputed to the first day of July of the year.

In the event the stop date of a medication is partial, the following imputation rules will be applied:

- If only day is missing, then the end date will be imputed as the last day of the month.
- If only year is non-missing, then the end date will be imputed as the last day of the year.

	SAP PAL-003 Amendment 1 version 1.0	Page 19
---	-------------------------------------	---------

All medications will be coded using the current version of the World Health Organization Drug (WHO Drug) dictionary (Sept. 2014). Prior and concomitant medication use will be summarized by Anatomical Therapeutic Chemical (ATC) medication class (Level 4) and preferred name (i.e., generic medication name) using descriptive statistics separately. A subject reporting the same medication more than once will be counted once when calculating the number and percentage of subjects who received that medication. A subject listing of prior and concomitant medications all subjects received will be provided.

	SAP PAL-003 Amendment 1 version 1.0	Page 20
---	-------------------------------------	---------

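### SAP Section 10 sets some incomplete start dates to the first dose date even when the recorded stop is earlier, so pre-treatment records can be counted as concomitant or treatment-emergent

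*SAP*

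**What the plan says.** Section 10 of the SAP sends a start date to the first dose date by three routes.

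1. **Start completely missing:** it is "imputed as the first dose date if the stop date is in the same year or later than the first dose date".
2. **Only the year known, equal to the first-dose year:** the first dose date is used, under the rule that begins "If year is the same as the year of first dose of pegvaliase then the start date will be imputed".
3. **Only the day missing, in the first-dose month:** the first dose date is used, under the rule that begins "If month is the same as the month of first dose of pegvaliase then the start date will be imputed".

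Two further rules cover starts before the period of first dose. A day-missing start is "imputed as the last day of the month, if the year and month is prior to the first dose year and month". A year-only start goes to 1 July, under the rule that begins "If year is before the year of first dose of study drug then the start date will be imputed to the first day".

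Partial stop dates are moved late. For a stop without a day, the rule is "If only day is missing, then the end date will be imputed as the last day of the month". For a stop with nothing but a year, it is "If only year is non-missing, then the end date will be imputed as the last day of the year".

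Concomitant medications are "any medications initially taken on or after the initial pegvaliase administration date", so the class depends on the start date.

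Section 14 applies the Section 10 rules to partial onset and end dates of adverse events. It treats any event with a missing onset as treatment-emergent. The same section defines a treatment-emergent event as one that first appeared or worsened after study drug began.

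**The concern.** Imputing an unknown start to the first dose is a sensible conservative default when the record might have overlapped treatment. It is not conservative when the stop date shows that the record ended before treatment; it then contradicts recorded data. Nothing in the SAP says that a stop before first dose overrides the imputation, or that an imputed start may not fall after the stop.

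For medications, a drug stopped before treatment can appear in the concomitant table. It may also be lost from the prior table if the program uses the imputed start. That loss is not certain, because the prior definition turns on when the drug was taken.

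For adverse events, an event that was over before treatment can enter the treatment-emergent tables. Section 14 also plans time to first onset and duration for events of special interest and sponsor-defined events of significance. A misdated event of that kind with partial onset would have its onset on the first dose day and a zero or negative duration. Safety is a secondary objective (Section 3.1). Section 3 gives the SAP precedence over the protocol where they differ, so protocol wording would not displace these rules.

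**Working it through.** The SAP gives no figure to reproduce. The check applies the Section 10 rules literally to example records. The dates are assumed, with first dose on 20 October 2009.

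**The wording of route 1.** A stop after first dose already satisfies the second half of the condition. The same-year half therefore adds only stops in the first-dose year that fall on or before the first dose date. Apart from a stop on that very day, these are the records that should not be imputed to first dose.

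**Examples.** Duration = stop − imputed start + 1.

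| Recorded start | Recorded stop | Stop used | Imputed start | Duration (days) | Concomitant by start? |
|---|---|---|---|---|---|
| Oct 2009 (route 3) | 5 Oct 2009 | 5 Oct | 20 Oct | −15 + 1 = −14 | yes, wrongly |
| missing or 2009 (routes 1, 2) | 25 Sep 2009 | 25 Sep | 20 Oct | −25 + 1 = −24 | yes, wrongly |
| missing or 2009 | Sep 2009 | 30 Sep | 20 Oct | −20 + 1 = −19 | yes, wrongly |
| missing, 2009 or Oct 2009 | Oct 2009 | 31 Oct | 20 Oct | 11 + 1 = 12 | yes, acceptable |
| missing, 2009 or Oct 2009 | 2009 | 31 Dec | 20 Oct | 72 + 1 = 73 | yes, acceptable |
| Aug 2009 | 5 Aug 2009 | 5 Aug | 31 Aug | −26 + 1 = −25 | no, but start after stop |
| 2008 | 10 Mar 2008 | 10 Mar 2008 | 1 Jul 2008 | −113 + 1 = −112 | no, but start after stop |

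The stops of 5 October, 25 September and 30 September fall 15, 25 and 20 days before first dose. They lie inside the prior-medication window, which reaches back 30 days before screening, however short screening was. The last two rows reverse the dates without reclassifying the record.

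**Bounds from the rules alone.**
- Routes 1 and 2: a stop the day before first dose gives −1 + 1 = 0. A stop on 1 January with first dose on 31 December gives −364 + 1 = −363, or −364 in a leap year.
- Route 3: a stop on the 1st with first dose on the 31st gives −30 + 1 = −29.

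**Exhaustive check.** In a 365-day year there are 365 × 364 / 2 = 66,430 pairs with the stop before first dose. Routes 1 and 2 set the start to first dose in all 66,430. For a first dose on 15 June, that is 165 possible stop dates under routes 1 and 2, and 14 under route 3. With a missing start and a stop in an earlier year, route 1 does not impute to first dose, so its check screens out earlier years only.

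**Adverse events.** Routes 2 and 3 carry over to partial onsets. Route 1 does not, because Section 14 has its own missing-onset rule, and that rule has no end-date condition. An event that ended before first dose cannot have appeared or worsened after it, so the rule conflicts with Section 14's own definition.

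**Effect on a table.** Each subject counts once per medication, so one wrong record moves a percentage by at most 100/N: 100/50 = 2.0 points, or 100/150 = 0.7 points (both N assumed).

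**The case against.** The best counter-case is that this is a rare edge case in descriptive tables.

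- **Route 1 does look at the stop date.** True, but by calendar year only. Routes 2 and 3 do not look at it at all.
- **The adverse-event part is an ambiguity.** Section 14 restricts the summaries to treatment-emergent events occurring during the study period, and a programmer could let a recorded end date prevail. This part also needs pre-dose events to have been recorded. Both points stand as limits. The SAP does not say which date prevails, however, and the missing-onset rule as written admits events that ended before treatment.
- **Negative durations are not reported for medications.** Correct. Section 10 plans counts and percentages only, so for medications the day counts show how far a date is displaced. Duration matters for the Section 14 events of interest. Among those, injection-site reactions cannot precede the first injection.
- **The extreme bounds are unrealistic for medications.** Largely correct. A stop many months before first dose lies in the prior window only if screening was long. The examples within 30 days do not depend on that.
- **The effect is diluted.** A subject who took the same drug at any time on treatment is counted anyway, and the planned listings let a reader see the record. The summary tables would still be wrong for other subjects.
- **The earlier-month and earlier-year rules reclassify nothing.** Agreed. They are a secondary date-consistency fault that the same correction removes.

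**Conclusion.** The point holds. Followed literally, Section 10 classes as concomitant some medications recorded as stopped before first dose. Section 14 can admit adverse events that ended before first dose to the treatment-emergent tables. Confidence is high for the medication rules as written. The adverse-event consequence depends on pre-dose events being recorded and, for partial onsets, on the program following the imputed onset.

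The reach is limited. No blood Phe result is touched; only descriptive medication and safety summaries are. The number of affected records cannot be known from the SAP and is probably small. The day counts and the 100/N figure give the size of an error per record, not its frequency. It should be corrected before programming because it is a stated rule that gives a wrong answer and is simple to repair.

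**What to change.** In Section 10, to apply after stop-date imputation, add:

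- The start is set to the first dose date only when the stop is on or after that date, missing, or continuing.
- No imputed start may be later than the stop. Where a rule would give a later date, use the stop date. This also repairs the earlier-month and earlier-year rules.
- If the start is wholly missing and the stop is before first dose, leave the start missing and classify the record by its stop.
- A medication whose recorded or imputed stop is before first dose is not concomitant. It is prior only if it meets the existing prior definition.

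In Section 14, add:

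- An adverse event whose recorded or imputed end is before first dose is not treatment-emergent.
- The missing-onset rule applies only when the end date is missing, ongoing, or on or after first dose.

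Applied to three test records that fail under the present rules (first dose 15 June 2010; stop 10 March 2010 under routes 1 and 2; stop 8 June 2010 under route 3), a stop-date condition plus the cap on the start makes all three prior only and not treatment-emergent.

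The cost is a few sentences and a few lines of code. Truly ambiguous records stay concomitant or treatment-emergent, so the conservative intent is kept.
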